Assessment of the effect of treatment will be based on a non-randomized, open-labeled, prospective study of intravenously administered Omegaven[®] fat emulsion to determine safety and preliminary efficacy in the treatment of PN associated liver injury. This treatment group will be compared to a group based on historical controls, i.e., a subset of patients (those whose direct bilirubin levels was ever > 2 mg/dL) previously studied by Andorsky et al.(31) This study included neonates treated between 1986 and 1996 who depended on parenteral nutrition for at least 90 days after surgical therapy for congenital or acquired intestinal diseases. Our study will primarily follow the patients included in Andorsky et al. study from 2 months before direct bilirubin first reached a level > 2 mg/dL (baseline date) until 2 months after patients either reached 3 consecutive bilirubin levels \leq 2 mg/dL or reached one bilirubin level \leq 2 mg/dL and were weaned from PN died, or underwent a liver transplant. In our exploratory analyses, we will include the entire available follow-up time in Andorsky et al. dataset for each patient.

b. Patient Selection and Inclusion/Exclusion Criteria

Omega-3 Fat Emulsion (Omegaven[®])

After the diagnosis of PNALD is made, patients who are followed by the Clinical Nutrition Service (CNS) or General Surgery Program, in conjunction with the patient's primary physician, will contact [name] or [name] and an evaluation will be performed. Cases may also include referrals of patients with PNALD from other healthcare facilities or self-referrals. If the patient's parents or guardians agree to participate in the study, informed consent will be obtained. The history of present illness and past medical history will be reviewed with the guardian and pertinent demographic and medical information will be recorded on data collection forms. This form will be used to record all laboratory results, nutritional history, and descriptions of any liver biopsies performed.

Though most patients receiving parenteral nutrition do not develop end stage liver disease, there is a small percentage of patients, typically infants and children on prolonged courses of parenteral nutrition, who do go on to develop fulminate liver failure. The study population of this protocol is limited to patients felt to fulfill any one of the following conditions:

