Generally, primary safety analyses will be based on time from baseline or 30 days after baseline until two months after patients first reached direct bilirubin levels $< 2\text{mg/dL}$. Baseline will be defined as information collected at the date that treatment starts for Omegaven[®] patients and on the date that patient reached bilirubin levels > 2 for soybean oil fat emulsion patients. Information on mortality and transplant will be collected during the whole treatment with Omegaven[®] and during the whole period for which we have data available in the Andorsky et al. dataset. Primary efficacy analysis will include time from baseline until the patient normalizes bilirubin (presents three consecutive direct bilirubin $\leq 2\text{ mg/dL}$ or a direct bilirubin $\leq 2\text{ mg/dL}$ and weaned from TPN). With exploratory purpose, we will also describe the curve of the several markers for the entire period that Andorsky et al. recorded data.

Outcome/Endpoints

1. Treatment safety

Our primary outcome for treatment safety will be based on patient's essential fatty acid profile. We will compare patients before treatment with Omegaven[®] started and after treatment started (one month after treatment started until treatment stopped) with respect to the frequency with which triene/tetraene ratio > 0.2 at any time. We will also compare the occurrence any event of of hypertriglyceridemia (serum triglyceride $> 400\text{mg/dL}$) between Omegaven[®] and soybean oil fat emulsions. Primary analyses for these and all other safety outcomes will be based on a follow-up time for Omegaven[®] and soybean oil fat emulsions starting 30 days after baseline, i.e., 30 days after treatment started for Omegaven[®] patients and 2 months after the first direct bilirubin level $< 2\text{ mg/dL}$ was recorded. We will also explore comparisons including the time from baseline until the end of follow-up period.

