Analysis of Baseline Characteristics

For statistical purposes, baseline values will be defined as the last measurement before starting to administer Omegaven® for patients, in the treatment group, and as the measurement taken when a patient first had a direct bilirubin level > 2 mg/dL recorded, in the historical control group. Descriptive statistics for all baseline relevant risk factors will be summarized for Omegaven® (omega-3 based fat emulsion) and historical control (soybean oil fat emulsion) groups. Associations between categorical predictors and Omegaven® vs. soybean oil fat emulsion groups will be tested through chi-square tests. Associations between continuous predictors and treatment groups will be studied through means (and standard deviations) and t-tests, or medians (and interquartile ranges) and Wilcoxon tests, when appropriate.

Analysis of Safety and Tolerability of Omegaven®

All primary safety and tolerability analyses will be based on descriptive statistics. In secondary analyses, we will also assess the statistical significance of differences. Some safety and tolerability outcomes will be measured only in the Omegaven® group. For those, we will compare results before starting PN with Omegaven® (while receiving PN with soybean oil fat emulsions) with after starting PN with Omegaven®. The period receiving Omegaven® will start to be counted 30 days after beginning PN with Omegaven® for the main analysis. Outcomes measured in the Omegaven® and soybean oil fat emulsion groups will be described separately for each of those groups for a period starting 30 days after baseline, i.e., 30 days after starting PN with Omegaven®, for the treatment group, and 30 days after bilirubin > 2 mg/dL, for the soybean oil fat emulsion group.

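### The endpoint section's explanation of when primary safety follow-up starts gives controls what looks like the end rule, contradicting its own 30-day rule and the analysis plan

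*Combined protocol and SAP*

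**What the plan says.** Four places bear on the primary safety window.

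- **Section 4e, opening paragraph.** Safety time runs from baseline, or from "30 days after baseline until two months after patients first reached direct bilirubin levels" below 2 mg/dL. Control baseline is set "on the date that patient reached bilirubin levels > 2 for soybean oil fat emulsion patients".
- **Section 4e, Treatment safety.** For hypertriglyceridemia and all other safety outcomes, follow-up is given for Omegaven and "soybean oil fat emulsions starting 30 days after baseline". The sentence then explains that start as "30 days after treatment started for Omegaven[®] patients and 2 months after the first direct bilirubin level" below 2 mg/dL.
- **Section 5c, baseline and safety analyses.** Control baseline is defined "as the measurement taken when a patient first had a direct bilirubin level > 2 mg/dL recorded, in the historical control group". The control safety period begins "30 days after bilirubin > 2 mg/dL, for the soybean oil fat emulsion group".
- **Study design paragraph, just before Patient Selection.** Primary follow-up of the historical controls continues "until 2 months after patients either reached 3 consecutive bilirubin levels" at or below 2 mg/dL. The alternatives listed there are one such level with weaning from PN, death, or liver transplant.

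**The concern.** The Treatment safety sentence names two groups, gives one start rule and then offers two dates to explain it. The first date is assigned to Omegaven. The second is left, by position, to the controls, and it falls after cholestasis has resolved. Section 5c starts the same period shortly after cholestasis begins.

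The start date fixes which control events and how much control time enter the between-group safety summaries. An outcome such as any triglyceride above 400 mg/dL depends directly on how long each child is observed. The controls are historical, so the window will be applied to records whose outcomes already exist. A start rule with two printed versions leaves a choice that the plan should have closed.

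**Working it through.** The plan gives no figure to reproduce, and no power or sample-size result uses this window. The check is date arithmetic.

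**Notation.** Day 0 is control baseline (direct bilirubin above 2 mg/dL). T is the day of the first direct bilirubin below 2 mg/dL. Two months is taken as about 60 days.

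**Control start and end dates as printed**

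| Source | Start | End |
|---|---|---|
| 4e, opening paragraph | day 0 or day 30 | T + 60 |
| 4e, Treatment safety, general rule | day 30 | not restated |
| 4e, Treatment safety, explanation | T + 60 | not restated |
| 5c, safety analysis | day 30 | not restated |
| Study design paragraph | not a safety start rule | 2 months after three consecutive values at or below 2, or the listed alternatives |

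**Step 1: do the start rules agree?** The general rule in 4e, combined with its own control baseline, gives day 30. Section 5c gives day 30. The explanation gives T + 60. The gap is (T + 60) − 30 = T + 30 days.

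**Step 2: length with the 4e explanation and the 4e end.** (T + 60) − (T + 60) = 0 days for every T.

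**Step 3: length with the 5c start and the 4e end.** (T + 60) − 30 = T + 30 days. For assumed T of 30, 90 and 180 days, the window is 60, 120 and 210 days. The documents give no distribution for T, so these values are illustrative only.

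**Step 4: length with the 4e explanation and the study design end.** Section 4f says the control data were abstracted at two-week intervals. Suppose the first value below 2 is also the first of the three consecutive values and there is no rebound. The third value then falls at T + 28.

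- Clock from the first of the three: (T + 60) − (T + 60) = 0 days.
- Clock from the third: (T + 28 + 60) − (T + 60) = 28 days.

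The window is therefore about 0 to 4 weeks, depending on which value starts the clock, and all of it lies after recovery.

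**Step 5: controls who never fall below 2 mg/dL.** T does not exist, so the explanation gives them no start date. Children who die or are transplanted while still cholestatic would be among them. The 4e end rule also gives them no end date.

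**Step 6: could an inequality sign explain it?** If the explanation meant above 2, controls would start at about day 60. That still differs from day 30 in the same sentence and in 5c, so a changed sign does not remove the conflict.

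**The case against.** The strongest reply is that the plan already contains the right rule. The Treatment safety sentence says 30 days after baseline before it goes on to explain itself. With the control baseline in 4e, that is the section 5c rule exactly, and 5c is unambiguous. The odd clause matches the end rule in the opening paragraph of 4e almost point for point, and it never names the controls. A lost control-start phrase and a lost 'until' would account for it, and 4e and 5c would then agree. An analyst who met an empty control window would notice at once and turn to 5c.

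Most of this stands. A reader might infer that the plan intends to compare Omegaven with recovered controls, or that the two sections cannot be reconciled. The documents support neither: a drafting slip is the likelier explanation. Nor can an empty window and a comparison with recovered controls both hold. The first follows from the end rule in 4e, the second from the one in the study design paragraph. A reader might also try to put a percentage on the lost control time, or argue that it comes from the worst phase of cholestasis. The documents give no basis for either. T is unknown, control baseline is the first crossing of 2 mg/dL, and hypothesis 2.1 expects controls to stay high over time.

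The reach is also limited. Section 5c makes the primary safety analyses descriptive. Section 4e adds exploratory comparisons from baseline, collects mortality and transplant over a longer period, and in its additional comparisons counts bloodstream infection and anaphylaxis from baseline.

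What the reply does not remove is that the reconciling words are not printed. The clause sits in the definition of the primary safety window, and nothing in the plan says which section prevails.

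**Conclusion.** The point holds as an inconsistency in a stated analysis rule. Read as the control start, the explanatory clause in 4e conflicts with its own sentence and with 5c by T + 30 days. Taken literally it yields 0 days of control safety time under the 4e end rule, or about 0 to 4 weeks after recovery under the study design end rule. Children who never fall below 2 mg/dL get no start date.

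This rests on reading the second date as belonging to the controls, which follows from the sentence structure and not from an explicit label. The 0 to 4 weeks further assumes two-weekly values and no rebound.

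The consequence is confined to the descriptive between-group safety outcomes that use this window, with triglycerides above 400 mg/dL the clearest case. The primary efficacy analysis is unaffected. So is the within-Omegaven triene/tetraene comparison, which has its own period, and so are the power figures in Tables 4 and 5. The clause needs correcting because it is wrong as written. It does not show that the safety comparison was designed to favor either group.

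**What to change.** In section 4e, Treatment safety, replace the explanatory clause with one start rule that matches section 5c: 30 days after treatment start for Omegaven, and 30 days after the first direct bilirubin above 2 mg/dL for controls.

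In a separate sentence, state one end rule for both groups and repeat it, or refer to it, in section 5c. This means reconciling two printed versions: two months after the first value below 2 mg/dL (section 4e), and two months after three consecutive values at or below 2 mg/dL or the listed alternatives (study design paragraph). The sentence should say which of the three values starts the clock, use one inequality throughout, and say when follow-up ends for children who never reach the threshold.

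The cost is a sentence or two of text. No new data are needed, and the sample size and power tables do not change.

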2.1 – Our primary hypothesis is that, after reaching bilirubin levels > 2 mg/dL, patients receiving Omegaven® will reach a bilirubin level ≤ 2 mg/dL faster than patients receiving conventional fat emulsions. Additionally, while patients receiving Omegaven™ will experience a decrease in their levels of bilirubin and other hepatic enzymes over time, patients receiving conventional emulsions will maintain high levels of bilirubin and other hepatic enzymes over time.

2.2 – Patients with surgical gastrointestinal disease and cholestasis will have better clinical hepatic outcomes than patients receiving conventional emulsions.

2.3 – Since patients receiving Omegaven® will have improved immune function, they will have a lower infection rate than patients receiving conventional fat emulsions.

2.4 – Due to a better general hepatic condition, patients receiving Omegaven® will also experience lower occurrence of liver transplant, death from hepatic associated causes, and blood transfusions.

2. Background and Significance

Parenteral Nutrition Associated Liver Disease (PNALD)

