Additional comparisons across treatment periods for subjects receiving Omegaven® will be aimed to assess occurrence of spontaneous bleeding (e.g., unexplained bruising, oozing from gums/incision sites), and maximum triene/tetraene ratio, minimum platelets, and maximum international normalized ratio (INR), trends in pre-albumin (age standardized levels). We will also explore trends in coagulopathies based on curves of platelets, prothrombin time (PT), partial thromboplastin time (PTT) over time, and INR. We will also describe the rate with which INR ratios were > 2 (number of days/follow-up time), as a marker of coagulopathies.

Additional comparisons between Omegaven® and soybean oil fat emulsion groups will be performed with regards to rate in which albumin is > 3 g/dL, maximum triglyceride level, rate of blood stream infections (number of positive blood cultures/follow-up-time under PN after baseline), rate of central venous catheter (CVC) infections (number of CVC infections/follow-up time and number of gram positive CVC infections/follow-up time), and occurrence of anaphylactic reactions after baseline.

Nutritional outcomes between Omegaven® and soybean oil fat emulsion groups that will be compared include changes in weight- and height-for-age Z-scores from baseline to 10% PN or cessation of PN..

We will describe trends over time for all outcomes associated with fatty acid profiles (including triene/tetraene ratios, triglycerides, total omega-6 fatty acids, total omega-3 fatty acids, total saturated, total monounsaturated, and total polysaturated fatty acids). Specific fatty acids such as arachidonic, palmoleic, palmitic, oleic, stearic, and linoleic fatty acids will also be evaluated and described. Also, for exploratory purposes, we will compare the trend in weight- and height-for-age Z-scores between both groups.

2. Omegaven®

3. The patient will complete treatment with Omegaven® in this study when he/she is completely off PN, develops a contraindication for further use, or the patient/family requests to be removed from the study.

f. Data Collection Methods, Assessments and Schedule

Omega-3 Fat Emulsion (Omegaven™)

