Data will be collected by the PI (MP), the managing co-investigator (KG), and the clinical coordinator with the assistance of the nursing unit liaisons and research assistants in [name] laboratory. Hospital charts will be reviewed for pertinent clinical information. Results of liver biopsies and blood chemistries will be obtained from PowerChart within the Cerner computer system at CHB. Specifically, the history of present illness, past medical history, and birth history, pertinent physical exam findings including patient weight, the results of liver biopsies, and parenteral and enteral feeding history will be collected. The information will be recorded on hard copy data collection forms.

Soybean based Fat Emulsion (Intralipid® and/or Liposyn®)

Data will be extracted from the Excel spread sheet used to store data of the Andorsky et al. study. Additionally, we will obtain information about date of birth (to estimate age at each visit and nutritional safety outcomes) and blood transfusions in Power Chart within the Cerner computer system at CHB. In the original study performed by Andorsky et al., data was abstracted from charts, nursing flowsheets (for nutritional intake data), and outpatient visit notes in two week intervals.

g. Study Timeline (as applicable)

This study will end when the results of an FDA approved clinical trial proves Omegaven® treatment to be ineffective or the product is approved for use in the United States. The investigators proposal to the Orphan Products Grants Program of FDA submitted in spring 2007 which was accepted.

h. Adverse Event Criteria and Reporting Procedures

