Primary outcomes measured only in the Omegaven® group will include whether the triene/tetraene ratio was ever > 0.2 during the intervention period and whether the INR was ever > 2. Secondary outcomes measured only on the Omegaven® group will include platelets, prothrombin time (PT), partial thromboplastin time (PTT), and other components of the fatty acid profile. Analysis of all categorical outcomes will be based on proportions and of all continuous outcomes will be based on means or medians of the individual mean, maximum or minimum values, as appropriate, during the respective follow-up period. Comparisons between periods (pre and post-treatment) will be performed based on paired tests, parametric or non-parametric, as appropriate. We will also explore trends over time (e.g., decreasing for INR and increasing for pre-albumin) and estimate p-values via regression models using generalized estimating equations or random effects to account for within subject correlations. When describing outcomes over time, we will explore the effect of predictors of poor hepatic outcomes, such as use of antifungal agents (e.g., amphotericin) and antidiarrheal agents (e.g., loperamide), on potential spikes.

Primary outcomes measured in the Omegaven® and soybean based fat emulsion groups will include whether triglycerides were ever > 400mg/dL, whether albumin was ever > 3, any occurrence of unexpected bleeding and number of times it occurred, occurrence of any anaphylactic reaction, rate of blood stream infections as shown by positive blood cultures, rate of line infections and gram positive central venous catheter infections. Outcomes will be summarized for each study group based proportions, poisson rates, mean, minimum, or maximum over the subject follow-up period, and statistical significance of differences between groups will be estimated with exploratory purpose via Fisher's exact test, Wilcoxon or t-tests, as appropriate.

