We will also describe individual profiles over time (i.e., 2 months before baseline or birth until end of follow-up period) for all subjects using graphical methods. Trends in liver function markers over time will be explored using generalized linear models in which correlations of observations within subjects will be accounted using a generalized equations or random effects approach. In these models we will hypothesize that for both groups biochemical levels increase for all tests with equal slope before treatment. After treatment, however, levels should be decreasing for patients in the Omegaven® group. We will perform these analyses including only subjects who did not die or undergo transplantation and including all subjects but assigning for subjects who died or underwent a transplant their worse possible outcome after they died or had the transplant. Using descriptive statistics, we will also explore the association between spikes in blood tests over time and predictors including transfusions of red blood cell products and blood stream infections.

Assessment of efficacy will be also based on comparison of means (or medians) of the mean and maximum modified PELD scores of each subject across all follow-up weeks. Adjustments of these comparisons for potential confounders will be based on linear regression models. Mean rates of infection will be compared using logrank and Cox proportional hazards models. Proportions of liver transplant, mortality, and red blood cell product transfusion events between the two groups will be compared via Fisher's exact test (or Chi-square tests, when appropriate). Adjustments for potential confounders will be considered using exact stratified analysis and logistic regression models.

Missing Values

Since data will be prospectively collected in the Omegaven® group, we anticipate that data will be nearly complete, particularly for the safety outcomes. In both groups, we will explore imputing any laboratory values that are missing up to two visits in the middle of the follow-up period using linear or non-linear interpolation, as appropriate. To interpolate direct and total bilirubin, we will primarily use the two closest observations, since bilirubin could be very different in points in time located further apart from the missing observation. We will compare conclusions of analyses based on imputed values with analyses based on the available information.

Potential Study Limitations

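### The blood stream infection rate counts positive cultures rather than infection episodes, and uses a different denominator from the catheter infection rate, so the between-group ratio can reflect repeat culturing or recording

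*Combined protocol and SAP*

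**What the plan says.** The infection rates are defined in section e (Definition of Primary and Secondary Outcomes/Endpoints, item 1, Treatment safety). For blood stream infection the plan specifies the "rate of blood stream infections (number of positive blood cultures/follow-up-time under PN after baseline"). The same sentence defines the CVC rates as "number of CVC infections/follow-up time and number of gram positive CVC infections/follow-up time". The numerator changes from cultures to infections, and the denominator from time on PN to follow-up time.

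Section 5c (Analysis of Safety and Tolerability) lists, among the primary outcomes measured in both groups, the "rate of blood stream infections as shown by positive blood cultures". It adds: "Outcomes will be summarized for each study group based proportions, poisson rates, mean, minimum, or maximum over the subject follow-up period". Significance is to be "estimated with exploratory purpose via Fisher's exact test, Wilcoxon or t-tests, as appropriate".

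The efficacy part of section 5c has a separate analysis: "Mean rates of infection will be compared using logrank and Cox proportional hazards models". The event for it is not defined. Hypothesis 2.3 is that, for Omegaven patients, "they will have a lower infection rate than patients receiving conventional fat emulsions".

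Section f (Data Collection Methods) says the main controls' data come from the earlier study's spreadsheet, built from charts, nursing flowsheets and "outpatient visit notes in two week intervals". The only additions it names are date of birth and transfusions. Omegaven data are collected from hospital charts as the study proceeds.

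**The concern.** A rate labelled as infections should count infections. With positive cultures as the numerator, a bacteraemia with three positive cultures scores three and one cultured once scores one. No section gives an episode definition, a window for merging repeat positives or a same-organism rule.

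In a single cohort this would mainly add noise. Here the groups come from different periods and data sources, so the number of recorded positives per episode may differ between them. That difference passes straight into the rate ratio. A true reduction of the kind hypothesis 2.3 predicts could be hidden, or a difference could appear where there is none.

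The second denominator adds a smaller problem. Follow-up time can include days off PN, when catheter exposure may be lower or absent, so the two infection rates are not on a common scale.

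**Working it through.** The documents state no infection rate, rate ratio or power for this endpoint, so there is no plan figure to reproduce. Table 5 concerns proportions of patients with an event and does not bear on it.

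**Numerator.** Let λ be the true episode rate per PN-day and m the mean number of recorded positive cultures per episode. The expected culture-based rate is λ × m, so

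observed ratio = (λ₁/λ₂) × (m₁/m₂).

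With equal true rates the observed ratio is m₁/m₂. The values of m below are assumptions; the documents give none.

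| m, group 1 | m, group 2 = 1 | 1.5 | 2 | 3 |
|---|---|---|---|---|
| 1 | 1.00 | 0.67 | 0.50 | 0.33 |
| 1.5 | 1.50 | 1.00 | 0.75 | 0.50 |
| 2 | 2.00 | 1.33 | 1.00 | 0.67 |
| 3 | 3.00 | 2.00 | 1.50 | 1.00 |

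Either group may be the one with more recorded positives, so the error can run either way. A true halving can also vanish: 0.5 × (2/1) = 1.0. Counting episodes sets m = 1 in both groups, and the ratio returns to λ₁/λ₂.

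**Precision.** A simulation used equal true episode rates, 20 or 30 patients per group (sizes from Tables 4 and 5), and assumed values of 60 or 120 days each and 5 or 10 episodes per 1000 PN-days. That is 20 × 60 × 0.005 = 6 to 30 × 120 × 0.01 = 36 expected episodes per group. Cultures per episode were 1 + Poisson(m − 1). The test was a two-sided 5% Wald test on the log Poisson rate ratio. False-positive rates were:

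- episodes counted: 2.5% to 5.0%;
- cultures counted, m equal (2 vs 2, or 3 vs 3): 20% to 31%, because repeat cultures are over-dispersed although the ratio is unbiased;
- cultures counted, 2 vs 1.5: 20% to 40%;
- cultures counted, 3 vs 1.5: 44% to 92%.

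The plan names Poisson rates as a summary, but Fisher, Wilcoxon or t-tests for significance. These percentages apply only if the Poisson rates are tested directly. The bias in the ratio when m differs does not depend on the test.

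**Denominator.** Section e runs the safety window to two months after direct bilirubin first falls below 2 mg/dL, and normalisation may coincide with weaning from PN. Off-PN days can therefore enter. As an illustration, take weaning at normalisation, 60 days off PN, and 60 to 180 days on PN (assumed). The off-PN share is 60/120 = 50% down to 60/240 = 25%. If no catheter infection occurs off PN, the rate per follow-up day is (1 − share) times the rate per PN-day. Equal shares cancel in the group ratio. Shares of 25% and 50% would give 0.75/0.50 = 1.5, or 0.67 with the groups reversed.

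**The case against.** The strongest reply is that section 5c can naturally be read as culture-confirmed infections, and that section 5b promises case report forms with clear definitions, which are not shown. Episodes may be counted in practice. That makes the plan ambiguous but does not resolve it: section e states the culture count outright, and nothing says which reading governs.

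A reader might go further and infer that the comparison does measure culturing practice across eras, with Omegaven's rate inflated because every culture is visible in a current record. The documents do not support this. They do not describe culture frequency in any period, do not list cultures among the Omegaven data items, and do not say how the control spreadsheet stored infections. Two-week abstraction makes collapsed records possible, not established. The multipliers above are assumptions, and the direction is unknown.

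Several features reduce the weight of the point, and all of them stand. Section e names the fatty acid profile as the primary safety outcome and places infection rates among additional comparisons. Section 5c makes the primary safety analyses descriptive and the group tests exploratory. Potential Study Limitations acknowledges changed care and reporting, and commits to a before/after comparison within Omegaven patients, which takes out the contrast with historical controls. The 1999-2004 controls narrow the gap in time. The log-rank/Cox analysis would be immune to repeat cultures if it uses time to first infection, though its event is undefined.

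On the denominator, follow-up time may be shorthand for the PN time just mentioned, patients may still be on PN when the window closes, and bias needs unequal off-PN shares. That limits this part to a request for one stated denominator.

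**Conclusion.** The point holds as a defect of definition. Section e counts positive cultures under the name of infections, section 5c can be read differently, and the CVC rates in the same sentence use another unit and another denominator. Because the groups differ in period and data source, the between-group ratio can be multiplied by the ratio of recorded positive cultures per episode. With an assumed 1 to 3 per episode in each group, that factor lies between 0.33 and 3. Neither its size nor its direction can be learned from the documents, so no claim is made that either emulsion is favoured. The denominator mismatch biases the comparison only if off-PN shares differ between groups. The wording should be corrected before analysis. It does not threaten the primary efficacy or primary safety outcome.

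**What to change.** In section e and section 5c, replace the numerator with blood stream infection episodes. Merge positive cultures within a pre-stated window, for example 14 days from an episode's first positive, which matches the main controls' abstraction interval. Add a same-organism rule where both datasets record the organism. Apply the rule identically to Omegaven and both control cohorts, and name the same event in the log-rank/Cox infection analysis.

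Use one denominator for blood stream, CVC and gram-positive CVC infection rates: PN-days, or catheter-days where both groups record them. Report raw positive-culture counts by group as a sensitivity check.

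The cost is protocol and SAP wording plus a de-duplication step, provided the control records carry usable dates; this should be checked first. Distinct infections inside the window would count once, and a bacteraemia lasting longer than the window would count again. The rule can be no finer than the date resolution of the control records. It also does not correct for episodes found only because more cultures were drawn.
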